4.3.1 Analysis of Demographics and Procedural Characteristics

Descriptive statistics will be generated for baseline demographics, procedural characteristics, and follow-up data collected. Categorical variables will be analyzed using frequency, incidence and event rate. For continuous variables collected in the study, analysis will include mean, median, standard deviation and range.

4.3.2 Analysis of Primary Endpoint

The primary endpoint for this study is TVF, which is defined as a composite of cardiac death, target vessel MI, or clinically driven TVR by percutaneous or surgical methods within 3 years post-procedure.

No formal statistical test will be performed, as this study is descriptive only. The TVF rate at 3 years and the exact two-sided 95% confidence intervals will be provided. In addition, the TVF at 3 years will be estimated for all ITT subjects by generating the two-sided 95% confidence

interval of the Kaplan-Meier estimate of the primary endpoint rate; subjects not experiencing the endpoint will be censored at 3 years post-procedure or day of withdrawal, whichever is earlier. Finally, the same analysis will be carried out on the PP population (secondary analysis).

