## 12.3 Primary Endpoint and Sample Size Calculation

The null hypothesis for this study states that the NIRxcell will have a primary endpoint rate greater than or equal to 34.8%. The alternative hypothesis states that the NIRxcell will have a primary endpoint rate less than 34.8%.

Specifically:

$$H_0: \pi_{\text{NIRTRAKS}} \geq 34.8\%$$

$$H_A: \pi_{\text{NIRTRAKS}} < 34.8\%$$

where  $\pi_{\text{NIRTRAKS}}$  is the true primary endpoint rate for the study stent and the 34.8% is the meta-analytically derived performance goal (PG) for the primary endpoint rate. Rejection of the null hypothesis will signify that the performance goal has been met, and that the study stent's primary endpoint rate is less than 34.8%.

The primary hypothesis test will be carried out by comparing the upper bound of the exact 1-sided 95% confidence interval of the 3-year TVF rate to 34.8%, the PG. If this upper bound is less than 34.8%, then it will be considered that the study stent meets the performance goal. The necessary sample size for testing the primary hypothesis was estimated with PASS software using exact hypothesis testing based on the exact distribution with the following assumptions:

- Type I error ( $\alpha$ ) = 0.05 (1-sided).
- Statistical power ( $1 - \beta$ ) = 83%.
- PG = 34.8%.
- $\pi_{\text{NIRTRAKS}} = 23.2\%$ .

An evaluable sample size of 105 provides 83% power to reject the above null hypothesis in favor of the alternative. Thus, 131 subjects will be enrolled to account for loss to follow-up, which is expected to be approximately 7.0% per year.

The loss to follow-up in previously published stent trials with long-term follow-up is low. In the SIRIUS trial, complete data compliance for all 5-year follow-up end points was 93.6% and 94% in the intervention and control groups, respectively. At 9 months the clinical compliance was 100% in both groups. In the ENDEAVOR II trial, out of 1,197 enrolled subjects, 1,167 were followed for 4 years (97.4%). In the RAVEL trial, complete data sets were available for 94.2% of subjects randomly assigned to sirolimus-eluting stents and for

94.1% of subjects randomized to BMS. In the TAXUS IV trial, out of 1,314 intention-to-treat (ITT) subjects, 5-year data were available for 1,294 (98.4%) subjects. In view of these data, we believe a yearly 7% loss-to-follow-up estimate is conservative and encompasses wide margins of safety.

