## 12.8 Handling of Missing Data in the Analysis of the Primary Endpoint

The primary analysis set will be the ITT population, which includes all subjects enrolled into the study. Subjects who prematurely withdraw prior to the 3-year (minus the allowable 1-month window) contact and prior to experiencing the primary endpoint will have their missing primary endpoint result handled using the following 3 approaches; results will be compared across the 3 approaches for consistency:

1. Only subjects with appropriate follow up (at least 3 years minus 1 month) or who experienced the primary endpoint by 3 years will be included in the exact hypothesis testing, as discussed above. This is the primary analysis..
2. Multiple imputation: This will be used to impute primary endpoint status (yes/no) for subjects with missing primary endpoint data. The logistic regression approach to multiple imputation will be carried out using SAS PROC MI. The covariates to be used in the imputation model will be age, sex, prevalence of diabetes, target lesion length and reference vessel diameter. Five data sets will be imputed, and a 1-sided test of the above null hypothesis will be carried out on each data set using the normal approximation to the binomial distribution. SAS PROC MIANALYZE on the results of the 5 significance tests will then be used to obtain an overall assessment of the significance of the 1-sided test across the 5 data sets.
3. As a third analysis and as discussed above, the Kaplan-Meier estimate of the 3-year primary endpoint rate, and its 1-sided upper 95% confidence interval will be calculated. Subjects not experiencing the primary endpoint within 3 years will be

censored at 3 years or the date of withdrawal from the study, whichever is earlier. The upper confidence limit will be compared to 34.8%; if less than 34.8%, the primary endpoint rate will be considered to be significantly less than the performance goal in this analysis.

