All subjects enrolled in the study are considered eligible for follow-up and will be required to adhere to the follow-up schedule outlined in Section 2.2.6. If a subject cannot be contacted for a follow-up assessment and follow-up information cannot be obtained, he/she will be counted as “missed contact” for that specific schedule. Attempts shall be made to contact the subject in next follow-up schedule. A subject will be considered “lost to follow-up” only after the last scheduled follow-up assessment for that subject (3 years). If a subject is lost to follow-up, the methods used to attempt to contact the subject should be documented. At least 3 attempts should be made to contact the subject through all available routes, and a certified letter should be sent to the permanent address in file.

Figure 1 summarizes the above steps and follow-up period.

Figure 1: Study Flowchart

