4.2.2 Per-Protocol

Per-protocol (PP) analysis will also be conducted. Per-protocol is defined as all subjects who sufficiently comply with the study protocol. Compliance covers treatment received, availability of follow-up data (follow-up of at least 3 years, allowing for a visit window of 3 years \pm 1 month), and absence of major protocol deviations.

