4.3.3 Analysis of Secondary Endpoints

All secondary endpoints (listed below) are dichotomous variables. Secondary endpoints will be presented as the number and percentage of subjects experiencing the outcome, along with two-sided exact 95% confidence intervals of the percentages. Included in the denominators for each outcome will be patients experiencing the event within the period (e.g., 30 days for 30-day time point, 270 days for 9-month time point, 365 days for 1-year time point, 730 days for 2-year time point, and 1095 days for 3-year time point) or who have adequate follow-up (e.g., at least 16 days for 1-month time point, at least 240 days for the 9-month time point, at least 335 days for the 1-year time point, at least 700 days for 2-year time point, and at least 1065 days for 3-year time point).

In addition, a Kaplan-Meier (K-M) estimate of the event-free survival rate and its corresponding standard error will be presented for cardiac death, target vessel MI, clinically driven TLR and TVR, with a corresponding K-M curve.

The secondary endpoints that will be reported are as follows:

1. **TVF** at 9 Months.
2. **All cause death** at 30 days, and 1, 2 and 3 years.
3. **Cardiac death** at 30 days, and 1, 2 and 3 years.
4. **All cause MI** at 30 days, and 1, 2 and 3 years.
5. **Target vessel MI** at 30 days, and 1, 2 and 3 years.
6. **Clinically driven TLR** at 30 days, and 1, 2 and 3 years.
7. **Clinically driven TVR** at 30 days, and 1, 2 and 3 years.
8. **Acute success rates**

Device success: Attainment of <50% final residual stenosis of the target lesion using the NIRxcell Stent System only.

Lesion success: Attainment of <50% final residual stenosis of the target lesion using any percutaneous method.

Procedure success: Attainment of <50% residual stenosis of the target lesion and no in-hospital death, MI or TLR.

9. **Stent thrombosis** at hospital discharge, at 30 days, and 1, 2 and 3 years.

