4.4 Adverse Events

A Treatment Emergent Adverse Event (TEAE) is an event that emerges, or a pre-existing event that worsens, any time during or after stent implantation. Adverse events will be coded by the MedDRA system version 18.1 or later. The per-event and per-patient incidence of TEAEs will be presented overall and by MedDRA system organ class and preferred term. This will be repeated for serious TEAEs.

5 TABLES, FIGURES, and LISTINGS

Table 1.1a Primary Endpoints – Intention-to-Treat Analysis Set

Primary Endpoint	ITT Subjects with Available Data (N=xx subjects)	Two-sided Binomial Exact 95% CI
TVF at 3 years	xx.xx% (xx/xx)	[xx.xx%, xx.xx%]
Cardiac Death	xx.xx% (xx/xx)	[xx.xx%, xx.xx%]
Target Vessel MI	xx.xx% (xx/xx)	[xx.xx%, xx.xx%]
Clinically-driven TVR	xx.xx% (xx/xx)	[xx.xx%, xx.xx%]

Note: Events defined for the period of 3 year post-procedure follow up are reported for patients with at least 1050 days of follow-up or with event to 3 years (1080 days).

Table 1.1b Primary Endpoints – Per-Protocol Analysis Set

Table 1.2 Secondary Endpoints – Intention-to-Treat Analysis Set

	ITT Subjects (N=xx subjects)	Two-sided Binomial Exact 95% CI
TVF at 9 months	xx.xx% (xx/xx)	[xx.xx%, xx.xx%]
All Cause Death		
30-day	xx.xx% (xx/xx)	[xx.xx%, xx.xx%]
1-year	xx.xx% (xx/xx)	[xx.xx%, xx.xx%]
2-year	xx.xx% (xx/xx)	[xx.xx%, xx.xx%]
3-year	xx.xx% (xx/xx)	[xx.xx%, xx.xx%]
Cardiac Death		
30-day	xx.xx% (xx/xx)	[xx.xx%, xx.xx%]
1-year	xx.xx% (xx/xx)	[xx.xx%, xx.xx%]
2-year	xx.xx% (xx/xx)	[xx.xx%, xx.xx%]
3-year	xx.xx% (xx/xx)	[xx.xx%, xx.xx%]
All Cause MI		
30-day	xx.xx% (xx/xx)	[xx.xx%, xx.xx%]
1-year	xx.xx% (xx/xx)	[xx.xx%, xx.xx%]
2-year	xx.xx% (xx/xx)	[xx.xx%, xx.xx%]
3-year	xx.xx% (xx/xx)	[xx.xx%, xx.xx%]
Target Vessel MI		
30-day	xx.xx% (xx/xx)	[xx.xx%, xx.xx%]
1-year	xx.xx% (xx/xx)	[xx.xx%, xx.xx%]
2-year	xx.xx% (xx/xx)	[xx.xx%, xx.xx%]
3-year	xx.xx% (xx/xx)	[xx.xx%, xx.xx%]
Clinically-driven TLR		
30-day	xx.xx% (xx/xx)	[xx.xx%, xx.xx%]
1-year	xx.xx% (xx/xx)	[xx.xx%, xx.xx%]
2-year	xx.xx% (xx/xx)	[xx.xx%, xx.xx%]
3-year	xx.xx% (xx/xx)	[xx.xx%, xx.xx%]
Clinically-driven TVR		
30-day	xx.xx% (xx/xx)	[xx.xx%, xx.xx%]

1-year	xx.xx% (xx/xx)	[xx.xx%, xx.xx%]
2-year	xx.xx% (xx/xx)	[xx.xx%, xx.xx%]
3-year	xx.xx% (xx/xx)	[xx.xx%, xx.xx%]
Device Success ¹	xx.xx% (xx/xx)	[xx.xx%, xx.xx%]
Lesion Success ²	xx.xx% (xx/xx)	[xx.xx%, xx.xx%]
Procedure Success ³	xx.xx% (xx/xx)	[xx.xx%, xx.xx%]
Stent Thrombosis		
Discharge	xx.xx% (xx/xx)	[xx.xx%, xx.xx%]

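### The Kaplan-Meier estimate of 3-year TVF has no last-contact censoring date, so subjects who silently stop responding count as event-free to 3 years

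*SAP*

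**What the plan says.** SAP 4.3.2 plans two ITT estimates of 3-year TVF: a crude rate with an exact interval, and a Kaplan-Meier estimate covering all ITT subjects. For the second, "subjects not experiencing the endpoint will be censored at 3 years post-procedure or day of withdrawal, whichever is earlier". Protocol 12.7 has the same rule, and Protocol 12.8 repeats it: "censored at 3 years or the date of withdrawal from the study, whichever is earlier". Neither document names a last-contact date.

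Under SAP 2.2.4, a subject who cannot be reached is a missed contact for that call. The site then tries again: "Attempts shall be made to contact the subject in next follow-up schedule". The subject becomes lost to follow-up "only after the last scheduled follow-up assessment for that subject (3 years"). The discontinuation list in the same section, and SAP Table 4, show loss to follow-up separately from withdrawal.

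Three related rules set the limits of the point:

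- The crude rate in SAP Table 1.1a is "reported for patients with at least 1050 days of follow-up or with event to 3 years (1080 days").
- The per-protocol set requires "follow-up of at least 3 years, allowing for a visit window of 3 years", with a one-month tolerance.
- SAP 4.3.3 says a Kaplan-Meier "estimate of the event-free survival rate and its corresponding standard error will be presented for cardiac death" and other components, with no censoring rule. The stent thrombosis curve (SAP Figure 3) has none either.

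**The concern.** Take a subject who answers the 9-month call, never answers again and never withdraws. There is no withdrawal date, and the lost-to-follow-up label arrives only after year 3. The rule then leaves one censoring date, 3 years, and more than two unobserved years enter the analysis as event-free time.

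Kaplan-Meier is used here to handle incomplete follow-up. It is also the only planned primary-endpoint estimate that covers every ITT subject. The multiple imputation in Protocol 12.8 is not in the current SAP, and Table 1.1a is restricted to subjects with available data. In a descriptive study the estimates and intervals are the result, so a rule that understates device failure and overstates precision should be corrected. The numbers at risk and censored under SAP Figure 2 would also make follow-up look more complete than it was.

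**Working it through.** **Inputs from the documents.** N = 65 and about 7.0% loss per year (SAP 4.1); planning TVF rate 23.2% (Protocol 12.3); contacts at 30 days, 9 months and 1, 2 and 3 years (SAP 2.2.6).

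**The plan's own figure.** 65 × 0.93³ = 52.3, which matches the stated 52 or so evaluable subjects.

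**Direction.** The Kaplan-Meier event rate is 1 − ∏(1 − dⱼ/nⱼ), with dⱼ events among nⱼ at risk at each event time. Keeping unobserved subjects in nⱼ shrinks each later dⱼ/nⱼ, so the estimate can only fall. It is unchanged only if no event follows a silent loss. An extreme case shows the mechanism: with 12 events and 13 subjects lost at day 0, last-contact censoring gives 12/52 = 23.1% (SE 5.8 points), and the rule as written gives 12/65 = 18.5% (SE 4.8).

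**Event timing.** Protocol 12.1 sets TVF₃ = 0.5·TVFₙ + TVFₙ/(n − 1). The year-1 share of 3-year events is therefore 0.5/(0.5 + 1/(n − 1)), which is 66.7% for n = 5 and 60% for n = 4.

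**Plausible loss.** The completeness figures in Protocol 12.3, annualised:

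- 1294/1314 over 5 years: 1 − 0.9848^(1/5) = 0.31%
- 1167/1197 over 4 years: 1 − 0.9749^(1/4) = 0.63%
- 94% over 5 years: 1.2%
- 94.1% over 3 years: 2.0%

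**Simulation.** 20,000 trials per scenario, N = 65, true TVF 23.2%, constant-hazard loss. The same observed events are analysed with censoring at last contact and with the rule as written.

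- Scenario A: two thirds of events in year 1, status known to the day of loss.
- Scenario B: half of events in year 1, status known only to the last scheduled call.

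| Loss per year | Silent share | A: last contact / as written | A gap (points) | B: last contact / as written | B gap (points) |
|---|---|---|---|---|---|
| 7% | all | 23.27% / 21.68% | −1.59 | 23.14% / 20.61% | −2.53 |
| 7% | half | 23.24% / 22.40% | −0.84 | 23.23% / 21.87% | −1.36 |
| 7% | quarter | 23.31% / 22.88% | −0.43 | 23.16% / 22.47% | −0.69 |
| 2% | all | 23.21% / 22.75% | −0.46 | 23.21% / 22.46% | −0.75 |
| 0.3% | all | 23.23% / 23.16% | −0.07 | 23.17% / 23.06% | −0.11 |

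At 7% all silent, about 11 of 65 subjects are event-free and unobserved at 3 years. The mean SE falls from 5.40 to 5.05 points in A and from 5.52 to 4.96 in B.

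A and B differ in two assumptions. A separate run of 3,000 trials, with half of events in year 1 and status known to the day of loss, falls between them: 23.2% against 21.2%. That set of runs also varied the true rate, using B's assumptions. At 10% it gave 10.0% against 8.9%, and at 34.8% it gave 34.9% against 31.0%. In none of its trials did the rule as written give a higher estimate or a higher SE.

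**Other estimates.** At 7% loss the crude rate (an event, or at least 1050 days of follow-up) averages 25.0% to 25.9%, so it is not understated.

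**Scale.** 52 × 0.232 ≈ 12 events. The exact 95% interval for 12/52 is 12.5% to 36.8%, about 24 points wide.

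**The case against.** The best defence is that withdrawal was meant broadly. Protocol 12.8 presents Kaplan-Meier as one way to handle everyone with a missing 3-year outcome and describes them all as withdrawing prematurely. On that reading silent losses are covered, and only a date is missing. The reading is possible, but it leaves no date to program, because loss is declared only after year 3. SAP Table 4 also lists loss apart from withdrawn consent. A programmer could simply use last contact, but the SAP's approval page says any deviation requires an amendment, so the rule should say so.

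The size can also be challenged, and much of that stands. The protocol says "we believe a yearly 7% loss-to-follow-up estimate is conservative". Sites must make repeated attempts by all routes and send a certified letter, and some subjects will be recaptured by a later call or through medical records. Those subjects are not affected. The 7% all-silent row is therefore an upper case, and half-silent loss at 2% per year gives only about 0.2 to 0.4 points. The estimate is also supplementary, the study makes no formal test, and Table 1.1a reports the crude rate.

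Finally, the SAP cites protocol version 3.0, and only version 1.2 was available. The later version could define withdrawal or last contact.

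**Conclusion.** The concern holds. As written, the rule biases the ITT Kaplan-Meier estimate of 3-year TVF downward and understates its standard error whenever a silent loss precedes an observed event. On the broader reading of withdrawal the censoring date is undefined, and the same correction is needed.

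The size depends on the loss rate and the silent share, and the documents do not give the share. It runs from about 0.1 point (0.3% annual loss) to 2.5 points (7% annual loss, all silent, half of events in year 1, status known only to the last call), at a true rate of 23.2% and N = 65. This is small beside the confidence interval and changes no test decision. The per-protocol estimate is unaffected. So is the crude rate, provided its follow-up days are counted to last contact, which the SAP does not state. It should be fixed because the error is avoidable and runs in the device's favour.

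**What to change.** In SAP 4.3.2, replace the censoring rule with: *Subjects without the endpoint are censored at the earliest of day 1095, date of withdrawal, or the last contact or assessment at which endpoint status was ascertained.*

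In addition:

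- State a matching rule for the component curves in SAP 4.3.3 and for Figure 3.
- Say that follow-up in the Table 1.1a denominator is counted to last contact.
- Add a footnote giving the number censored before 3 years because of missed contacts.
- Align the 3-year mark. SAP 4.3.3 uses days 1095 and 1065, while the Table 1.1a note uses 1080 and 1050 and Figure 2 stops at 1080.
- Check protocol version 3.0 for the wording found in sections 12.7 and 12.8 of version 1.2.

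How to treat non-cardiac death is a separate choice and is not part of this change.

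The cost is a few sentences and one count. Each scheduled contact already has its own case report form, so no new data are needed. The downside is a slightly wider confidence interval.

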4.3.3 Analysis of Secondary Endpoints

All secondary endpoints (listed below) are dichotomous variables. Secondary endpoints will be presented as the number and percentage of subjects experiencing the outcome, along with two-sided exact 95% confidence intervals of the percentages. Included in the denominators for each outcome will be patients experiencing the event within the period (e.g., 30 days for 30-day time point, 270 days for 9-month time point, 365 days for 1-year time point, 730 days for 2-year time point, and 1095 days for 3-year time point) or who have adequate follow-up (e.g., at least 16 days for 1-month time point, at least 240 days for the 9-month time point, at least 335 days for the 1-year time point, at least 700 days for 2-year time point, and at least 1065 days for 3-year time point).

In addition, a Kaplan-Meier (K-M) estimate of the event-free survival rate and its corresponding standard error will be presented for cardiac death, target vessel MI, clinically driven TLR and TVR, with a corresponding K-M curve.

The secondary endpoints that will be reported are as follows:

1. **TVF** at 9 Months.
2. **All cause death** at 30 days, and 1, 2 and 3 years.
3. **Cardiac death** at 30 days, and 1, 2 and 3 years.
4. **All cause MI** at 30 days, and 1, 2 and 3 years.
5. **Target vessel MI** at 30 days, and 1, 2 and 3 years.
6. **Clinically driven TLR** at 30 days, and 1, 2 and 3 years.
7. **Clinically driven TVR** at 30 days, and 1, 2 and 3 years.
8. **Acute success rates**

Device success: Attainment of <50% final residual stenosis of the target lesion using the NIRxcell Stent System only.

Lesion success: Attainment of <50% final residual stenosis of the target lesion using any percutaneous method.

Procedure success: Attainment of <50% residual stenosis of the target lesion and no in-hospital death, MI or TLR.

9. **Stent thrombosis** at hospital discharge, at 30 days, and 1, 2 and 3 years.

4.4 Adverse Events

A Treatment Emergent Adverse Event (TEAE) is an event that emerges, or a pre-existing event that worsens, any time during or after stent implantation. Adverse events will be coded by the MedDRA system version 18.1 or later. The per-event and per-patient incidence of TEAEs will be presented overall and by MedDRA system organ class and preferred term. This will be repeated for serious TEAEs.

5 TABLES, FIGURES, and LISTINGS

Table 1.1a Primary Endpoints – Intention-to-Treat Analysis Set

Primary Endpoint	ITT Subjects with Available Data (N=xx subjects)	Two-sided Binomial Exact 95% CI
TVF at 3 years	xx.xx% (xx/xx)	[xx.xx%, xx.xx%]
Cardiac Death	xx.xx% (xx/xx)	[xx.xx%, xx.xx%]
Target Vessel MI	xx.xx% (xx/xx)	[xx.xx%, xx.xx%]
Clinically-driven TVR	xx.xx% (xx/xx)	[xx.xx%, xx.xx%]

Note: Events defined for the period of 3 year post-procedure follow up are reported for patients with at least 1050 days of follow-up or with event to 3 years (1080 days).

Table 1.1b Primary Endpoints – Per-Protocol Analysis Set

Table 1.2 Secondary Endpoints – Intention-to-Treat Analysis Set

	ITT Subjects (N=xx subjects)	Two-sided Binomial Exact 95% CI
TVF at 9 months	xx.xx% (xx/xx)	[xx.xx%, xx.xx%]
All Cause Death		
30-day	xx.xx% (xx/xx)	[xx.xx%, xx.xx%]
1-year	xx.xx% (xx/xx)	[xx.xx%, xx.xx%]
2-year	xx.xx% (xx/xx)	[xx.xx%, xx.xx%]
3-year	xx.xx% (xx/xx)	[xx.xx%, xx.xx%]
Cardiac Death		
30-day	xx.xx% (xx/xx)	[xx.xx%, xx.xx%]
1-year	xx.xx% (xx/xx)	[xx.xx%, xx.xx%]
2-year	xx.xx% (xx/xx)	[xx.xx%, xx.xx%]
3-year	xx.xx% (xx/xx)	[xx.xx%, xx.xx%]
All Cause MI		
30-day	xx.xx% (xx/xx)	[xx.xx%, xx.xx%]
1-year	xx.xx% (xx/xx)	[xx.xx%, xx.xx%]
2-year	xx.xx% (xx/xx)	[xx.xx%, xx.xx%]
3-year	xx.xx% (xx/xx)	[xx.xx%, xx.xx%]
Target Vessel MI		
30-day	xx.xx% (xx/xx)	[xx.xx%, xx.xx%]
1-year	xx.xx% (xx/xx)	[xx.xx%, xx.xx%]
2-year	xx.xx% (xx/xx)	[xx.xx%, xx.xx%]
3-year	xx.xx% (xx/xx)	[xx.xx%, xx.xx%]
Clinically-driven TLR		
30-day	xx.xx% (xx/xx)	[xx.xx%, xx.xx%]
1-year	xx.xx% (xx/xx)	[xx.xx%, xx.xx%]
2-year	xx.xx% (xx/xx)	[xx.xx%, xx.xx%]
3-year	xx.xx% (xx/xx)	[xx.xx%, xx.xx%]
Clinically-driven TVR		
30-day	xx.xx% (xx/xx)	[xx.xx%, xx.xx%]

1-year	xx.xx% (xx/xx)	[xx.xx%, xx.xx%]
2-year	xx.xx% (xx/xx)	[xx.xx%, xx.xx%]
3-year	xx.xx% (xx/xx)	[xx.xx%, xx.xx%]
Device Success ¹	xx.xx% (xx/xx)	[xx.xx%, xx.xx%]
Lesion Success ²	xx.xx% (xx/xx)	[xx.xx%, xx.xx%]
Procedure Success ³	xx.xx% (xx/xx)	[xx.xx%, xx.xx%]
Stent Thrombosis		
Discharge	xx.xx% (xx/xx)	[xx.xx%, xx.xx%]
30-day	xx.xx% (xx/xx)	[xx.xx%, xx.xx%]
1-year	xx.xx% (xx/xx)	[xx.xx%, xx.xx%]
2-year	xx.xx% (xx/xx)	[xx.xx%, xx.xx%]
3-year	xx.xx% (xx/xx)	[xx.xx%, xx.xx%]

1 Device success is defined as attainment of <50% final residual stenosis of the target lesion using only the NIRxcell Stent System.

2 Lesion success is defined as attainment of <50% final residual stenosis of the target lesion using any percutaneous method.

3 Procedure success is defined as attainment of <50% residual stenosis of the target lesion and no in-hospital death, MI, or TLR.

Events in this table have been adjudicated by the CEC.

Denominators for 30-day events will reflect the number of patients with an adjudicated event in 30 days or follow-up through 16 days.

Denominators for 9-month events will reflect the number of patients with an adjudicated event in 270 days or follow-up through 240 days.

Denominators for 1-year events will reflect the number of patients with an adjudicated event in 365 days or follow-up through 335 days.

Denominators for 2-year events will reflect the number of patients with an adjudicated event in 730 days or follow-up through 700 days.

Denominators for 3-year events will reflect the number of patients with an adjudicated event in 1095 days or follow-up through 1065 days.

Table 2 Enrollment by Site

Site	Site Name	Site Location	ITT Subjects (N=xx subjects)	Per Protocol Subjects (N=xx subjects)
001			xx	xx
002			xx	xx
Total			xx	xx

Table 3 Compliance Table -- Intention-to-Treat Analysis Set

Site	Index Procedure Form	30-Day Contact ¹	9-Month Contact ²	1-Year Contact ³	2-Year Contact ⁴	3-Year Contact ⁵
	(received/expected, %)	(received/expected, %)	(received/expected, %)	(received/expected, %)	(received/expected, %)	(received/expected, %)
001	xx.xx% (xx/xx)	xx.xx% (xx/xx)	xx.xx% (xx/xx)	xx.xx% (xx/xx)	xx.xx% (xx/xx)	xx.xx% (xx/xx)
002	xx.xx% (xx/xx)	xx.xx% (xx/xx)	xx.xx% (xx/xx)	xx.xx% (xx/xx)	xx.xx% (xx/xx)	xx.xx% (xx/xx)
...
014						
015						
Total	xx.xx% (xx/xx)	xx.xx% (xx/xx)	xx.xx% (xx/xx)	xx.xx% (xx/xx)	xx.xx% (xx/xx)	xx.xx% (xx/xx)

1 Denominator for 30-Day contact includes patients who had 30-day visit form filled or patients who have reached 44 (30+14) days after procedure (data export date - procedure date) and excludes patients who died or withdrew before 44 days.

2 Denominator for 9-Month contact includes patients who had 9-month visit form filled or patients who have reached 300 (270+30) days after procedure (data export date - procedure date) and excludes patients who died or withdrew before 300 days.

3 Denominator for 1-year contact includes patients who had 1-year visit form filled or patients who have reached 395 (365+30) days after procedure (data export date - procedure date) and excludes patients who died or withdrew before 395 days.

4 Denominator for 2-year contact includes patients who had 2-year visit form filled or patients who have reached 760 (730+30) days after procedure (data export date - procedure date) and excludes patients who died or withdrew before 760 days.

5 Denominator for 3-year contact includes patients who had 3-year visit form filled or patients who have reached 1125 (1095+30) days after procedure (data export date - procedure date) and excludes patients who died or withdrew before 1125 days.

Table 4 Patient Disposition

	ITT Subjects (N=xx subjects)	Per Protocol Subjects (N=xx subjects)
	n (%)	n (%)
Enrolled	xx (xx.xx%)	xx (xx.xx%)
Completed the study	xx (xx.xx%)	xx (xx.xx%)
Not completed all required follow-up visits	xx (xx.xx%)	xx (xx.xx%)
Primary reason for not completed		
Withdrew consent	xx (xx.xx%)	xx (xx.xx%)
Lost to follow-up	xx (xx.xx%)	xx (xx.xx%)
Adverse event	xx (xx.xx%)	xx (xx.xx%)
Death	xx (xx.xx%)	xx (xx.xx%)
Lack of efficacy	xx (xx.xx%)	xx (xx.xx%)
Protocol violation	xx (xx.xx%)	xx (xx.xx%)
Physician decision	xx (xx.xx%)	xx (xx.xx%)
Study cancelled	xx (xx.xx%)	xx (xx.xx%)
Other	xx (xx.xx%)	xx (xx.xx%)

Table 5 Demographic and Medical History – Intention-to-Treat Analysis Set

Characteristics	ITT Subjects (N=xx subjects)	95% CI
Demographics		
Age (yrs)		
Mean±SD (N)	xx.xx±xx.xx (xx)	[xx.xx, xx.xx]
Median (Q1, Q3)	xx.xx (xx.xx, xx.xx)	
Range (min, max)	(xx.xx, xx.xx)	
Male	xx.xx% (xx/xx)	[xx.xx%, xx.xx%]
Ethnicity		
Hispanic or Latino	xx.xx% (xx/xx)	[xx.xx%, xx.xx%]
Not Hispanic or Latino	xx.xx% (xx/xx)	[xx.xx%, xx.xx%]
Race		
American Indian or Alaska Native	xx.xx% (xx/xx)	[xx.xx%, xx.xx%]
Asian	xx.xx% (xx/xx)	[xx.xx%, xx.xx%]
Black or African American	xx.xx% (xx/xx)	[xx.xx%, xx.xx%]
Native Hawaiian or Other Pacific Islander	xx.xx% (xx/xx)	[xx.xx%, xx.xx%]
White	xx.xx% (xx/xx)	[xx.xx%, xx.xx%]
Other	xx.xx% (xx/xx)	[xx.xx%, xx.xx%]
Medical History/Risk Factor		
Previous MI	xx.xx% (xx/xx)	[xx.xx%, xx.xx%]
Previous PCI	xx.xx% (xx/xx)	[xx.xx%, xx.xx%]
Previous CABG	xx.xx% (xx/xx)	[xx.xx%, xx.xx%]
Previous TIA	xx.xx% (xx/xx)	[xx.xx%, xx.xx%]
Previous CVA	xx.xx% (xx/xx)	[xx.xx%, xx.xx%]
Congestive Heart Failure	xx.xx% (xx/xx)	[xx.xx%, xx.xx%]
Family History of Premature Coronary Artery Disease (CAD)	xx.xx% (xx/xx)	[xx.xx%, xx.xx%]

Atrial Fibrillation	xx.xx% (xx/xx)	[xx.xx%, xx.xx%]
Chronic Lung Disease/COPD	xx.xx% (xx/xx)	[xx.xx%, xx.xx%]
Cancer	xx.xx% (xx/xx)	[xx.xx%, xx.xx%]
Mental Illness	xx.xx% (xx/xx)	[xx.xx%, xx.xx%]
Active GI Bleed	xx.xx% (xx/xx)	[xx.xx%, xx.xx%]
Diabetes Mellitus	xx.xx% (xx/xx)	[xx.xx%, xx.xx%]
Diet	xx.xx% (xx/xx)	[xx.xx%, xx.xx%]
Insulin	xx.xx% (xx/xx)	[xx.xx%, xx.xx%]
Oral Hypoglycemics	xx.xx% (xx/xx)	[xx.xx%, xx.xx%]
Peripheral Vascular Disease	xx.xx% (xx/xx)	[xx.xx%, xx.xx%]
Hypertension	xx.xx% (xx/xx)	[xx.xx%, xx.xx%]
Hypercholesterolemia	xx.xx% (xx/xx)	[xx.xx%, xx.xx%]
Chronic Renal Disease	xx.xx% (xx/xx)	[xx.xx%, xx.xx%]
Receiving Dialysis	xx.xx% (xx/xx)	[xx.xx%, xx.xx%]
Current Smoking Status		
Current Smoker	xx.xx% (xx/xx)	[xx.xx%, xx.xx%]
Former Smoker	xx.xx% (xx/xx)	[xx.xx%, xx.xx%]
Never Smoked	xx.xx% (xx/xx)	[xx.xx%, xx.xx%]
LVEF at most recent evaluation prior to index procedure		
Mean±SD (N)	xx.xx±xx.xx (xx)	[xx.xx, xx.xx]
Median (Q1, Q3)	xx.xx (xx.xx, xx.xx)	
Range (min, max)	(xx.xx, xx.xx)	

Table 6 Procedural Characteristic – Intention-to-Treat Analysis Set

Characteristics	ITT Subjects (N=xx subjects)	95% CI
Procedural Characteristic		
Time of Procedure (min)		
Mean±SD (N)	xx.xx±xx.xx (xx)	[xx.xx, xx.xx]
Median (Q1, Q3)	xx.xx (xx.xx, xx.xx)	
Range (min, max)	(xx.xx, xx.xx)	
Vascular Access Site		
Femoral	xx.xx% (xx/xx)	[xx.xx%, xx.xx%]
Radial	xx.xx% (xx/xx)	[xx.xx%, xx.xx%]
Other	xx.xx% (xx/xx)	[xx.xx%, xx.xx%]
Number of Non-target Lesion treated		
0	xx.xx% (xx/xx)	[xx.xx%, xx.xx%]
1	xx.xx% (xx/xx)	[xx.xx%, xx.xx%]
2	xx.xx% (xx/xx)	[xx.xx%, xx.xx%]
3	xx.xx% (xx/xx)	[xx.xx%, xx.xx%]
Other Devices used for the Target Lesion		
Atherectomy Device	xx.xx% (xx/xx)	[xx.xx%, xx.xx%]
Laser Device	xx.xx% (xx/xx)	[xx.xx%, xx.xx%]
Cutting Balloon	xx.xx% (xx/xx)	[xx.xx%, xx.xx%]
Brachytherapy Device	xx.xx% (xx/xx)	[xx.xx%, xx.xx%]
Thrombectomy	xx.xx% (xx/xx)	[xx.xx%, xx.xx%]
Other	xx.xx% (xx/xx)	[xx.xx%, xx.xx%]
Vascular Closure Device used	xx.xx% (xx/xx)	[xx.xx%, xx.xx%]
Bailout Procedure Performed	xx.xx% (xx/xx)	[xx.xx%, xx.xx%]
Lesion Characteristic		
Target Vessel Location		
LMCA	xx.xx% (xx/xx)	[xx.xx%, xx.xx%]

LAD	xx.xx% (xx/xx)	[xx.xx%, xx.xx%]
LCX	xx.xx% (xx/xx)	[xx.xx%, xx.xx%]
RCA	xx.xx% (xx/xx)	[xx.xx%, xx.xx%]
Target Lesion treated	xx.xx% (xx/xx)	[xx.xx%, xx.xx%]
Native/ de novo Lesion	xx.xx% (xx/xx)	[xx.xx%, xx.xx%]
Pre-Procedure Diameter Stenosis (%)		
Mean±SD (N)	xx.xx±xx.xx (xx)	[xx.xx, xx.xx]
Median (Q1, Q3)	xx.xx (xx.xx, xx.xx)	
Range (min, max)	(xx.xx, xx.xx)	
Post-Procedure Diameter Stenosis (%)		
Mean±SD (N)	xx.xx±xx.xx (xx)	[xx.xx, xx.xx]
Median (Q1, Q3)	xx.xx (xx.xx, xx.xx)	
Range (min, max)	(xx.xx, xx.xx)	
Lesion Length (mm)		
Mean±SD (N)	xx.xx±xx.xx (xx)	[xx.xx, xx.xx]
Median (Q1, Q3)	xx.xx (xx.xx, xx.xx)	
Range (min, max)	(xx.xx, xx.xx)	
Reference Vessel Diameter (mm)		
Mean±SD (N)	xx.xx±xx.xx (xx)	[xx.xx, xx.xx]
Median (Q1, Q3)	xx.xx (xx.xx, xx.xx)	
Range (min, max)	(xx.xx, xx.xx)	
Tortuosity		
None	xx.xx% (xx/xx)	[xx.xx%, xx.xx%]
Mild	xx.xx% (xx/xx)	[xx.xx%, xx.xx%]
Moderate	xx.xx% (xx/xx)	[xx.xx%, xx.xx%]
Severe	xx.xx% (xx/xx)	[xx.xx%, xx.xx%]
Final Dissection Grade		
0	xx.xx% (xx/xx)	[xx.xx%, xx.xx%]
A	xx.xx% (xx/xx)	[xx.xx%, xx.xx%]
B	xx.xx% (xx/xx)	[xx.xx%, xx.xx%]
C	xx.xx% (xx/xx)	[xx.xx%, xx.xx%]
D	xx.xx% (xx/xx)	[xx.xx%, xx.xx%]

E	xx.xx% (xx/xx)	[xx.xx%, xx.xx%]
F	xx.xx% (xx/xx)	[xx.xx%, xx.xx%]
Pre-Procedure TIMI		
0	xx.xx% (xx/xx)	[xx.xx%, xx.xx%]
1	xx.xx% (xx/xx)	[xx.xx%, xx.xx%]
2	xx.xx% (xx/xx)	[xx.xx%, xx.xx%]
3	xx.xx% (xx/xx)	[xx.xx%, xx.xx%]
Post-Procedure TIMI		
0	xx.xx% (xx/xx)	[xx.xx%, xx.xx%]
1	xx.xx% (xx/xx)	[xx.xx%, xx.xx%]
2	xx.xx% (xx/xx)	[xx.xx%, xx.xx%]
3	xx.xx% (xx/xx)	[xx.xx%, xx.xx%]
Device Characteristics		
Reason for Deployment the study stent		
Treatment of Target Lesion	xx.xx% (xx/xx)	[xx.xx%, xx.xx%]
Treatment of Non-target Lesion	xx.xx% (xx/xx)	[xx.xx%, xx.xx%]
Treatment of complication (bailout)	xx.xx% (xx/xx)	[xx.xx%, xx.xx%]
Other	xx.xx% (xx/xx)	[xx.xx%, xx.xx%]
Pre-dilatation performed		
Maximum Balloon Diameter (mm)	xx.xx% (xx/xx)	[xx.xx%, xx.xx%]
Mean±SD (N)	xx.xx±xx.xx (xx)	[xx.xx, xx.xx]
Median (Q1, Q3)	xx.xx (xx.xx, xx.xx)	
Range (min, max)	(xx.xx, xx.xx)	
Maximum Balloon Length (mm)		
Mean±SD (N)	xx.xx±xx.xx (xx)	[xx.xx, xx.xx]
Median (Q1, Q3)	xx.xx (xx.xx, xx.xx)	
Range (min, max)	(xx.xx, xx.xx)	
Maximum Balloon Pressure (atm)		
Mean±SD (N)	xx.xx±xx.xx (xx)	[xx.xx, xx.xx]
Median (Q1, Q3)	xx.xx (xx.xx, xx.xx)	
Range (min, max)	(xx.xx, xx.xx)	
Stent Location Relative to Lesion		

At Target Lesion	xx.xx% (xx/xx)	[xx.xx%, xx.xx%]
Proximal to the Target Lesion	xx.xx% (xx/xx)	[xx.xx%, xx.xx%]
Distal to the Target Lesion	xx.xx% (xx/xx)	[xx.xx%, xx.xx%]
Other	xx.xx% (xx/xx)	[xx.xx%, xx.xx%]
Post-dilatation performed	xx.xx% (xx/xx)	[xx.xx%, xx.xx%]
Maximum Balloon Diameter (mm)		
Mean±SD (N)	xx.xx±xx.xx (xx)	[xx.xx, xx.xx]
Median (Q1, Q3)	xx.xx (xx.xx, xx.xx)	
Range (min, max)	(xx.xx, xx.xx)	
Maximum Balloon Length (mm)		
Mean±SD (N)	xx.xx±xx.xx (xx)	[xx.xx, xx.xx]
Median (Q1, Q3)	xx.xx (xx.xx, xx.xx)	
Range (min, max)	(xx.xx, xx.xx)	
Maximum Balloon Pressure (atm)		
Mean±SD (N)	xx.xx±xx.xx (xx)	[xx.xx, xx.xx]
Median (Q1, Q3)	xx.xx (xx.xx, xx.xx)	
Range (min, max)	(xx.xx, xx.xx)	
Outcome of Stent Deployment		
Stent Deployed	xx.xx% (xx/xx)	[xx.xx%, xx.xx%]
Failed Delivery/Misplaced Stent	xx.xx% (xx/xx)	[xx.xx%, xx.xx%]
Device Package opened, but not used	xx.xx% (xx/xx)	[xx.xx%, xx.xx%]
Maximum Stent Deployment Pressure		
Mean±SD (N)	xx.xx±xx.xx (xx)	[xx.xx, xx.xx]
Median (Q1, Q3)	xx.xx (xx.xx, xx.xx)	
Range (min, max)	(xx.xx, xx.xx)	
Second Stent placed at the Target Lesion	xx.xx% (xx/xx)	[xx.xx%, xx.xx%]
Overlapped with the Previous Stent	xx.xx% (xx/xx)	[xx.xx%, xx.xx%]

Table 7 Stent Implanted by Diameter and Length - Intention-to-Treat Analysis Set

Any Stent		
Characteristics	ITT Subjects (N=xx subjects, S=xx stents)	95% CI
Any Stent		
Diameter of Stent (mm)		
2.5	xx.xx% (xx/xx)	[xx.xx%, xx.xx%]
2.75	xx.xx% (xx/xx)	[xx.xx%, xx.xx%]
3.0	xx.xx% (xx/xx)	[xx.xx%, xx.xx%]
3.5	xx.xx% (xx/xx)	[xx.xx%, xx.xx%]
4.0	xx.xx% (xx/xx)	[xx.xx%, xx.xx%]
Length of Stent (mm)		
8	xx.xx% (xx/xx)	[xx.xx%, xx.xx%]
12	xx.xx% (xx/xx)	[xx.xx%, xx.xx%]
17	xx.xx% (xx/xx)	[xx.xx%, xx.xx%]
20	xx.xx% (xx/xx)	[xx.xx%, xx.xx%]
24	xx.xx% (xx/xx)	[xx.xx%, xx.xx%]
28	xx.xx% (xx/xx)	[xx.xx%, xx.xx%]
33	xx.xx% (xx/xx)	[xx.xx%, xx.xx%]

Any Stent	Diameter (mm)					
Length (mm)	2.5	2.75	3.0	3.5	4.0	Total
8	xx	Xx	Xx	xx	xx	xx
12	xx	Xx	Xx	xx	xx	xx
17	xx	Xx	Xx	xx	xx	xx
20	xx	Xx	Xx	xx	xx	xx
24	xx	Xx	Xx	xx	xx	xx
28	xx	Xx	Xx	xx	xx	xx
33	xx	Xx	Xx	xx	xx	xx
Total	xx	Xx	Xx	xx	xx	xx

Study Stent

Characteristics	ITT Subjects	
	(N=xx subjects, S=xx stents)	95% CI
Study Stent		
Diameter of Stent (mm)		
2.5	xx.xx% (xx/xx)	[xx.xx%, xx.xx%]
2.75	xx.xx% (xx/xx)	[xx.xx%, xx.xx%]
3.0	xx.xx% (xx/xx)	[xx.xx%, xx.xx%]
3.5	xx.xx% (xx/xx)	[xx.xx%, xx.xx%]
4.0	xx.xx% (xx/xx)	[xx.xx%, xx.xx%]
Length of Stent (mm)		
8	xx.xx% (xx/xx)	[xx.xx%, xx.xx%]
12	xx.xx% (xx/xx)	[xx.xx%, xx.xx%]
17	xx.xx% (xx/xx)	[xx.xx%, xx.xx%]
20	xx.xx% (xx/xx)	[xx.xx%, xx.xx%]
24	xx.xx% (xx/xx)	[xx.xx%, xx.xx%]
28	xx.xx% (xx/xx)	[xx.xx%, xx.xx%]
33	xx.xx% (xx/xx)	[xx.xx%, xx.xx%]

Length (mm)	Diameter (mm)					Total
	2.5	2.75	3.0	3.5	4.0	
8	xx	Xx	Xx	xx	xx	xx
12	xx	Xx	Xx	xx	xx	xx
17	xx	Xx	Xx	xx	xx	xx
20	xx	Xx	Xx	xx	xx	xx
24	xx	Xx	Xx	xx	xx	xx
28	xx	Xx	Xx	xx	xx	xx
33	xx	Xx	Xx	xx	xx	xx
Total	xx	Xx	Xx	xx	xx	xx

Non-Study Stent

Characteristics	ITT Subjects		95% CI	
	(N=xx subjects, S=xx stents)			
Non-Study Stent				
Diameter of Stent (mm)				
2.5	xx.xx% (xx/xx)		[xx.xx%, xx.xx%]	
2.75	xx.xx% (xx/xx)		[xx.xx%, xx.xx%]	
3.0	xx.xx% (xx/xx)		[xx.xx%, xx.xx%]	
3.5	xx.xx% (xx/xx)		[xx.xx%, xx.xx%]	
4.0	xx.xx% (xx/xx)		[xx.xx%, xx.xx%]	
Length of Stent (mm)				
8	xx.xx% (xx/xx)		[xx.xx%, xx.xx%]	
12	xx.xx% (xx/xx)		[xx.xx%, xx.xx%]	
17	xx.xx% (xx/xx)		[xx.xx%, xx.xx%]	
20	xx.xx% (xx/xx)		[xx.xx%, xx.xx%]	
24	xx.xx% (xx/xx)		[xx.xx%, xx.xx%]	
28	xx.xx% (xx/xx)		[xx.xx%, xx.xx%]	
33	xx.xx% (xx/xx)		[xx.xx%, xx.xx%]	

Non-Study Stent	Diameter (mm)						Total
	Length (mm)	2.5	2.75	3.0	3.5	4.0	
8	xx	Xx	Xx	xx	xx	xx	xx
12	xx	Xx	Xx	xx	xx	xx	xx
17	xx	Xx	Xx	xx	xx	xx	xx
20	xx	Xx	Xx	xx	xx	xx	xx
24	xx	Xx	Xx	xx	xx	xx	xx
28	xx	Xx	Xx	xx	xx	xx	xx
33	xx	Xx	Xx	xx	xx	xx	xx
Total	xx	Xx	Xx	xx	xx	xx	xx

Table 8 Baseline Angiographic Findings -- Intention-to-Treat Analysis Set

	ITT Subjects (N=xx subjects)	95% CI
Lesion Location		
Prox	xx.xx% (xx/xx)	[xx.xx%, xx.xx%]
Mid	xx.xx% (xx/xx)	[xx.xx%, xx.xx%]
Distal	xx.xx% (xx/xx)	[xx.xx%, xx.xx%]
Ostial	xx.xx% (xx/xx)	[xx.xx%, xx.xx%]
Lesion Length (mm)		
Mean±SD (N)	xx.xx±xx.xx (xx)	[xx.xx, xx.xx]
Median (Q1, Q3)	xx.xx (xx.xx, xx.xx)	
Range (min, max)	(xx.xx, xx.xx)	
Eccentric	xx.xx% (xx/xx)	[xx.xx%, xx.xx%]
Bend		
< 45 degrees	xx.xx% (xx/xx)	[xx.xx%, xx.xx%]
≥ 45 degrees and <90 degrees	xx.xx% (xx/xx)	[xx.xx%, xx.xx%]
≥ 90 degrees	xx.xx% (xx/xx)	[xx.xx%, xx.xx%]
Thrombus	xx.xx% (xx/xx)	[xx.xx%, xx.xx%]
Tortuosity		
Mild	xx.xx% (xx/xx)	[xx.xx%, xx.xx%]
Moderate	xx.xx% (xx/xx)	[xx.xx%, xx.xx%]
Severe	xx.xx% (xx/xx)	[xx.xx%, xx.xx%]
Calcification		
Mild	xx.xx% (xx/xx)	[xx.xx%, xx.xx%]
Moderate	xx.xx% (xx/xx)	[xx.xx%, xx.xx%]
Severe	xx.xx% (xx/xx)	[xx.xx%, xx.xx%]
Ulcerated	xx.xx% (xx/xx)	[xx.xx%, xx.xx%]
Aneurysm	xx.xx% (xx/xx)	[xx.xx%, xx.xx%]
Intimal Flap	xx.xx% (xx/xx)	[xx.xx%, xx.xx%]
Ectasia	xx.xx% (xx/xx)	[xx.xx%, xx.xx%]

Pre TIMI		
0	xx.xx% (xx/xx)	[xx.xx%, xx.xx%]
1	xx.xx% (xx/xx)	[xx.xx%, xx.xx%]
2	xx.xx% (xx/xx)	[xx.xx%, xx.xx%]
3	xx.xx% (xx/xx)	[xx.xx%, xx.xx%]
Bifurcation	xx.xx% (xx/xx)	[xx.xx%, xx.xx%]
Medina Bifurcation		
